## 7. STATISTICAL CONSIDERATIONS

### 7.1 Sample Size Considerations

This study will be performed with two cohorts 1) severe COVID-19 infection and 2) moderate COVID-19 infection (as defined in inclusion criteria).

The effect of the intervention will be evaluated in each cohort separately. A total of 32 patients will be enrolled in each cohort with a 3:1 allocation ratio (24 Etoposide and 8 control per cohort). Assuming a 30% response rate in the control group for the primary outcome of a 2 point improvement in respiratory status on an 8 point scale at Day 14, we can detect a 50% increase in response in the Etoposide group (80% response rate in the Etoposide group) with a 2-sided  $\alpha$  of 0.05 and 80% power. While this study is not powered to detect a statistically significant difference in outcome, it will provide initial evidence of efficacy if improvement in response is observed.

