### **3.2 Inclusion Criteria (applicable for patients enrolled for treatment or data collection)**

- Age 18 years or older
- Confirmed COVID-19 infection
- Evidence of cytokine storm defined as:
  - Peak ferritin > 10,000 ng/mL OR
  - Peak ferritin > 500 ng/mL and one or more of the following at any time during hospital admission:
    - Lactate dehydrogenase > 500 U/L, d-dimer > 1000 ng/mL, C-reactive protein > 100 mg/L, or WBC > 15 k/uL
- Cohort 1: Intubated status as a result of COVID infection-associated respiratory illness
- Cohort 2 (if activated): Evidence of progressive respiratory failure (requiring >4 L/min of supplemental oxygen to maintain SaO2 greater than 92%) without intubation

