## 8.2 Response Definitions

8-Point Ordinal Scale:

- 8 - Death;
- 7 - Ventilation in addition to extracorporeal membrane oxygen (ECMO), continuous renal replacement therapy (CRRT), or need for vasopressors (dopamine  $\geq 5$   $\mu$ g/kg/min OR epinephrine  $\geq 0.1$   $\mu$ g/kg/min OR norepinephrine  $\geq 0.1$   $\mu$ g/kg/min);
- 6 - Intubation and mechanical ventilation;
- 5 - Non-invasive mechanical ventilation (NIV) or high-flow oxygen;
- 4 - Hospitalized, requiring oxygen by mask or nasal prongs;
- 3 - Hospitalization without oxygen supplementation;
- 2 - Discharged from hospital either to home with supplemental oxygen OR to inpatient rehabilitation/skilled nursing facility (+/- supplemental oxygen);
- 1 - Discharged to home without supplemental oxygen

When calculating Ventilator Free days, reintubations or re-hospitalizations or death occurring in the first 28 days should result in zero ascribed to time off the ventilator prior to reintubation

When calculating days of hospitalization, re-hospitalization or death occurring in the first 28 days should result in zero ascribed to time out of the hospital prior to readmission.

When determining days of supplemental oxygen use and need for supplemental oxygen, the patient will only be considered to no longer need supplemental oxygen if a room air saturation is  $\geq 90\%$  after five minutes of rest.

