#### **9.5 Stopping Rules**

Accrual in a cohort will continue after the interim analysis if  $\geq 1$  of the treated patients in that cohort meets the primary endpoint of 2 point improvement in respiratory status on the 8 point scale at day 14. If cohort 1 is stopped, enrollment in cohort 2 (if open) may still continue.

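### Discharge home or to a rehabilitation or nursing facility scores 1 or 2 whatever its purpose, so a patient discharged there for end-of-life care and alive on Day 14 counts as a responder

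*Combined protocol and SAP*

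**What the plan says.** Section 7.1 sets the "primary outcome of a 2 point improvement in respiratory status on an 8 point scale at Day 14" as the basis for sample size, and Section 7.2 compares the response rates by Fisher's exact test among all randomized patients.

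The scale is in Section 8.2. It has two discharge levels:

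- Level 2: "Discharged from hospital either to home with supplemental oxygen OR to inpatient rehabilitation/skilled nursing facility (+/- supplemental oxygen".
- Level 1: "1 - Discharged to home without supplemental oxygen".

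Neither level refers to prognosis or goals of care, and neither the protocol nor its statistical sections mention hospice, comfort care or palliative discharge. Two in-hospital levels matter for comparison: "4 - Hospitalized, requiring oxygen by mask or nasal prongs", which is tied to being in hospital, and "6 - Intubation and mechanical ventilation", which names no place of care. Death is level 8.

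Section 3.2 fixes the entry levels. The first cohort is "Cohort 1: Intubated status as a result of COVID infection-associated respiratory illness", which is level 6 or 7. The second requires "Evidence of progressive respiratory failure" with more than 4 L/min of oxygen and no intubation, which is level 4 or 5.

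Under Section 9.5, accrual in a cohort goes on after the interim analysis if at least one "of the treated patients in that cohort meets the primary endpoint of 2 point improvement in respiratory status" at Day 14.

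**The concern.** A response on this endpoint is meant to show that the lungs have recovered. Leaving hospital usually shows that, but not when the purpose of discharge is to die elsewhere. Section 8.2 does not separate the two, so a treatment failure can be recorded as a success.

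The authors dealt with a related problem for other outcomes. Section 8.2 gives no credit for time off the ventilator or out of hospital before a death or readmission within 28 days. No such safeguard qualifies a discharge score on the primary endpoint.

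Two design features make an explicit rule more important. The trial is open-label with the investigator assessing the primary endpoint (Section 10.1), so any unwritten scoring choice falls to an unblinded assessor. And each cohort has only 8 controls, so one control scored wrongly moves the control rate by 1/8 = 12.5 percentage points. One in the etoposide arm moves that rate by 1/24 = 4.2 points.

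**Working it through.** **1. Scale arithmetic** (levels from Section 8.2, entry levels from Section 3.2)

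| Entry level | Gain if discharged at 2 | Gain if discharged at 1 |
|---|---|---|
| 7 (cohort 1) | 5 | 6 |
| 6 (cohort 1) | 4 | 5 |
| 5 (cohort 2) | 3 | 4 |
| 4 (cohort 2) | 2 | 3 |

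Every cell is at least 2, so every discharge to a listed destination is a response if the patient is alive on Day 14. A death by Day 14 scores 8 and cannot be a response.

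**2. The plan's own figure.** Section 7.1 states 80% power for 30% vs 80% with 8 and 24 patients, two-sided 0.05. With unpooled variance, SE = √(0.3×0.7/8 + 0.8×0.2/24) = 0.1814, 0.5/0.1814 = 2.756, and power = Φ(2.756 − 1.960) = 78.7%, close to the stated value. The exact power of the planned Fisher test is 67.9%. That gap is a separate matter; I use 67.9% as the baseline below.

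**3. One patient near the boundary** (two-sided Fisher)

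| Etoposide | Control | p |
|---|---|---|
| 16/24 | 2/8 | 0.096 |
| 17/24 | 2/8 | 0.038 |
| 17/24 | 3/8 | 0.116 |

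These tables were chosen at the boundary. Summing over all possible outcomes:

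- One extra etoposide responder turns a non-significant result significant in about 10% of trials at 80% vs 30%, and in about 1% at 30% vs 30%.
- One extra control responder removes significance in about 23% of trials at 80% vs 30%.

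**4. Direction.** Suppose a share m of true non-responders is scored as responders, so a true rate p becomes p + m(1 − p). The values of m are assumptions.

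Same m in both arms, true rates 30% and 80%:

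| m | Control | Etoposide | Difference (points) | Fisher power |
|---|---|---|---|---|
| 0 | 30% | 80% | 50 | 67.9% |
| 5% | 33.5% | 81% | 47.5 | 64.0% |
| 10% | 37% | 82% | 45 | 60.4% |
| 20% | 44% | 84% | 40 | 53.7% |

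Equal misscoring hides a benefit. If instead both true rates are 30% and only the etoposide arm is misscored, the chance of a significant result favouring etoposide rises from 1.0% (m=0) to 2.8% (m=10%) and 6.3% (m=20%).

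**5. How often.** The documents give no rate. If a proportion q of patients is in this state at Day 14, the chance of at least one among n is 1 − (1 − q)^n.

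| q (assumed) | n=10 | n=24 | n=32 |
|---|---|---|---|
| 1% | 10% | 21% | 28% |
| 2% | 18% | 38% | 48% |
| 4% | 34% | 62% | 73% |

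**6. The continuation rule.** Such a patient decides Section 9.5 only if no other treated patient responds. Ten enrolled patients (Section 9.4) in blocks of four at 3:1 give 7 or 8 treated; Section 7.2 speaks of 10 on etoposide. If treated patients truly respond at the 30% assumed for controls, the chance of no responder is 0.7^7 = 8.2% with 7, 0.7^8 = 5.8% with 8 and 0.7^10 = 2.8% with 10.

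**The case against.** The strongest reply is that the affected group is narrow. Day 14 mortality is recorded, so only patients discharged for end-of-life care and still alive then are misscored. Survival at 30 days is a key secondary endpoint, so later deaths among such responders would show. Section 7.1 itself says that the study is not powered for a significant difference, which limits how much a shift in the p-value means. All of this stands and keeps the point modest. It does not remove it: the same section treats an observed improvement in response as initial evidence of efficacy, so the definition of a response still matters.

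A reader might infer more than the documents support, in three ways.

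- **That every discharge scores 1 or 2.** Section 8.2 lists only home and rehabilitation or skilled nursing facilities. A hospice unit, long-term acute care or another hospital is not listed, so its score is undefined rather than favourable.
- **That a patient transferred while still ventilated is a responder.** Level 6 carries no restriction on place, and level 2 allows only for supplemental oxygen. Level 6 or 7 is the natural reading. What is missing is a tie-break, which is a minor clarification.
- **That the error favours etoposide, or that one such patient settles the result.** Nothing in the documents points to a direction, and steps 3 and 4 of the working show effects both ways and a change of significance in a minority of trials.

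**Conclusion.** The point holds in a limited form. As written, Section 8.2 counts a patient discharged home or to a rehabilitation or skilled nursing facility for end-of-life care, and alive on Day 14, as a responder in either cohort and either arm, and as one who can satisfy Section 9.5. This follows from the text alone and needs no assumption.

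The size is uncertain. It rests on a rate that the documents do not give, and the figures for m and q are illustrations. What can be said is that each such patient shifts an arm's rate by 12.5 points (control) or 4.2 points (etoposide), which can cross 0.05 near the boundary but usually would not. No figure stated in the plan is wrong because of this. It should be corrected because the remedy is cheap, and because a scoring rule written after outcomes are seen in an open-label trial would look data-driven.

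**What to change.** Add to Section 8.2, and apply in Sections 7.1 and 9.5: a patient discharged to hospice or for comfort care, or whose respiratory support was reduced as part of comfort care, is a non-responder at Day 14 whatever the scale category, in both arms.

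The rule should set the response status directly. Capping the score at the last in-hospital level is not enough: a patient extubated for comfort to nasal oxygen moves from 6 to 4 in hospital, already a 2-point gain, and may never be discharged.

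As a minor clarification, state that a patient still on invasive ventilation is scored 6 or 7 wherever cared for.

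Cost: the wording, plus discharge destination and intent from the chart. It also needs a Day 14 status check for discharged patients in both arms. The calendar in Section 6 names only mortality for Day 14, and Section 4.1 ends control follow-up at death or discharge, so the check should be added beside the Day 14 mortality assessment already planned. The response rate in either arm may become slightly less favourable. The rule concerns scoring only and changes no care.

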## 7.2 Statistical Analysis

Tabulations overall, and by treatment group, will be produced for appropriate demographic, baseline, efficacy, and safety parameters, with number and percentages reported for categorical variables and the mean, median, standard deviation, and range for continuous variables. All analyses will be performed at an  $\alpha=0.05$  level using SAS v.4.

Efficacy analyses will be performed in an intention-to-treat (ITT) population consisting of all patients randomized. The difference in ordinal scale improvement rates between treatment arms will be calculated with a 95% confidence interval and formally compared using Fisher's Exact Test. For secondary analysis of the primary endpoint, logistic models individually adjusted for age, diabetes, chronic lung disease/moderate or severe asthma, immunocompromise, liver disease, heart disease/hypertension, smoking and obesity (BMI  $> 40$ ), residence in long-term care facility, will also be examined with odds ratios and 95% confidence intervals reported.

The analysis of secondary time to event endpoints including survival at 30 days, duration of hospitalization, duration of ventilation and ventilator free days, will be compared between treatment arms based on a log-rank test. The median will be estimated with a 95% CI for each treatment arm using the Kaplan-Meier method. Cox proportional Hazards models adjusted individually for age, diabetes, chronic lung disease/moderate or severe asthma, immunocompromise, liver disease, heart disease/hypertension, smoking and obesity (BMI  $> 40$ ), residence in long-term care facility, will also be examined with odds ratios and 95% confidence intervals reported. Changes in inflammatory markers and in oxygenation or  $\text{paO}_2/\text{FIO}_2$  ratio, based on available recorded measurements, will be compared between treatment arms using a two sample t-test, or a Wilcoxon Rank Sum test, as appropriate. Incidence of grade 3 or 4 AEs and serious AEs will be compared using Fisher's Exact test.

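### The 80% power in section 7.1 does not hold for the planned Fisher's exact test: with 24 vs 8 patients it is 68%, and the next sentence disclaims power altogether

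*Combined protocol and SAP*

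**What the plan says.** Section 7.1 sets the design of each cohort: "A total of 32 patients will be enrolled in each cohort with a 3:1 allocation ratio (24 Etoposide and 8 control per cohort"). The cohorts are not pooled: "The effect of the intervention will be evaluated in each cohort separately". The planning rates follow: "Assuming a 30% response rate in the control group for the primary outcome of a 2 point improvement in respiratory status", assessed at Day 14. On that basis "we can detect a 50% increase in response in the Etoposide group (80% response rate in the Etoposide group"), with a two-sided alpha "of 0.05 and 80% power". No test or formula is named for this figure.

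The next sentence of section 7.1 begins: "While this study is not powered to detect a statistically significant difference in outcome". It goes on to say that an observed improvement would count as initial evidence of efficacy.

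Section 7.2 names the analysis. The response rates are to be "formally compared using Fisher's Exact Test", with a 95% confidence interval for their difference. On the population it says: "Efficacy analyses will be performed in an intention-to-treat (ITT) population consisting of all patients randomized".

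**The concern.** The power claim has to describe the test that will be run. Fisher's exact test is conservative in small, unbalanced samples, and 8 controls is a very small group, so a power figure from a large-sample formula will be too high for it. Section 7.1 names no method, so a reader will naturally attach the 80% to the test in section 7.2.

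The two consecutive sentences of section 7.1 also conflict. One says the design can detect a stated difference at alpha 0.05 with 80% power; the other says it is not powered to detect a significant difference.

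What is at stake is how a non-significant cohort result is read. Even if the assumed gain of 50 percentage points were real, about one cohort in three would miss significance, where the plan tells its reader to expect one in five. A reader who relies on the stated figure would take a null result as stronger evidence against etoposide than it is.

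**Working it through.** **Inputs, all from sections 7.1 and 7.2.** Etoposide n = 24, control n = 8; response 0.80 vs 0.30; two-sided alpha 0.05; each cohort tested alone; all randomized patients analysed; Fisher's exact test.

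**1. Where the 80% may come from.** Section 7.1 gives no method, so I tried the usual ones. For the normal approximation with unpooled variance:

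- SE = √(0.3×0.7/8 + 0.8×0.2/24) = √(0.02625 + 0.00667) = 0.1814
- Power = Φ(0.50/0.1814 − 1.96) = Φ(0.796) = 78.7%
- Controls needed for 80% power = (0.21 + 0.16/3) × (1.96 + 0.8416)² / 0.25 = 8.27, or 33.1 patients in total, against 32 planned

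This is the closest two-sided match. With pooled variance under the null:

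- Mean rate = (8×0.3 + 24×0.8)/32 = 0.675
- Null SE = √(0.675×0.325×(1/8 + 1/24)) = 0.1912
- Power = Φ((0.50 − 1.96×0.1912)/0.1814) = Φ(0.690) = 75.5%

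The arcsine approximation gives 73.4% and the continuity-corrected one 59.1%. A one-sided pooled calculation gives 84.7%, but the plan specifies a two-sided test.

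**2. Power of the planned test.** There are 25 × 9 possible outcome pairs. For each, compute the two-sided Fisher p-value, reject if p ≤ 0.05, and add up the probabilities under Binomial(24, 0.80) and Binomial(8, 0.30). In the direction favouring etoposide:

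| Control responders | Probability | Etoposide responders needed | Chance of reaching that | Product |
|---|---|---|---|---|
| 0 | 0.0576 | ≥10 | 1.000 | 0.0576 |
| 1 | 0.1977 | ≥14 | 0.996 | 0.1969 |
| 2 | 0.2965 | ≥17 | 0.911 | 0.2700 |
| 3 | 0.2541 | ≥20 | 0.460 | 0.1169 |
| 4 | 0.1361 | ≥21 | 0.264 | 0.0359 |
| 5 | 0.0467 | ≥23 | 0.033 | 0.0015 |
| 6 to 8 | 0.0113 | not possible | 0 | 0 |

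The products sum to 0.679. Rejections in the opposite direction add less than 0.000001. **Power is 67.9%**, and the type II error is 1 − 0.679 = 32.1%. The table shows why: 3 responders among 8 controls is only slightly above the expected 2.4, yet etoposide then needs at least 20 of 24, which has a 46% chance when the true rate is 80%.

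**3. Is this only a matter of which test?** Exact two-sided power at the same rates:

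| Test | Power |
|---|---|
| Fisher's exact (planned) | 67.9% |
| Fisher's, p-value as twice the one-sided tail | 62.6% |
| Boschloo's unconditional exact | 72.9% |
| Likelihood ratio | 74.5% |
| Pearson chi-square, uncorrected | 74.9% |
| Wald, unpooled | 75.1% |

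None reaches 80%. Fisher's true size is 2.8% at a common rate of 30%, and at most 3.1%, which is where much of its power goes.

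**4. What would give 80% with Fisher's test.**

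- Keeping 24 vs 8 and a 30% control rate: 77.7% at an etoposide rate of 84%, and 80.1% at 85%.
- Keeping 80% vs 30% and 3:1 allocation: 75.3% with 27 vs 9, 76.3% with 30 vs 10, and 81.7% with 33 vs 11, i.e. 44 per cohort.

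**5. Precision.** At the design rates the Wald 95% interval has half-width 1.96 × 0.1814 = 0.356, about 36 percentage points.

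**The case against.** The strongest reply is that the 80% is not a slip of arithmetic. An unpooled normal approximation on the plan's own inputs gives 78.7% and needs 33.1 patients against the 32 planned, so the figure probably came from a standard formula. That stands as an account of its likely origin, and the fault is best described as a mismatch between the power formula and the planned test. It does not rescue the figure: the approximation is itself just under 80%, and its 78.7% falls to 75.1% when the same Wald test is evaluated exactly.

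The second reply is that the plan disclaims power, promises only initial evidence, and will report a confidence interval that shows the imprecision. Nothing else in the protocol uses the power figure: continuation after the interim analysis needs only one responder among treated patients (section 9.5), and cohort 2 opens on committee review (section 4.2). This limits the practical harm. But the disclaimer supplies no corrected number, and as written it contradicts the sentence before it. It may have been meant for differences smaller than 50 points; the text does not say so.

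The wording about a 50% increase is a minor editorial matter. Read as a relative gain (30% to 45%), Fisher power would be about 7%, but the 80% given in the same clause rules that reading out. Whether a 50-point gain is realistic cannot be judged from the documents, and the finding does not depend on it.

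**Conclusion.** The concern holds. Under the plan's own sample size, rates, alpha and test, power per cohort is 67.9% and not 80%, a shortfall of 12 percentage points. No other two-sided test or approximation checked reaches 80%. The two power statements in section 7.1 cannot both stand as written.

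The result assumes that all 32 patients have a Day 14 outcome and that the two-sided Fisher p-value is the usual one, which sums all tables no more probable than the one observed. Section 7.1 states no allowance for missing outcomes, and missing data would change the figure. The interim rule has no material effect: with blocks of four at 3:1, the first 10 patients randomized include at least 7 allocated to etoposide, and the chance that none of 7 responds at an 80% rate is 0.2⁷, about 0.00001.

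**What to change.** In section 7.1, replace the power sentence with wording such as: *With 24 etoposide and 8 control patients per cohort and a two-sided Fisher's exact test at 0.05, power is about 68% for response rates of 80% vs 30% (a difference of 50 percentage points); 80% power is reached at about 85% vs 30%.*

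Then make the next sentence agree with it. Once the 80% is gone, a statement that the trial is not powered for smaller differences and is meant to give initial evidence can stay. Deleting the disclaimer and leaving the 80% would not be a correction.

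This costs wording only: no extra patients and no change to endpoint, allocation or test. The stated power becomes less favourable.

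Two alternatives are open to the sponsor, neither of them required. Keeping 80% power at 80% vs 30% with Fisher's test would take about 33 vs 11, which is 44 − 32 = 12 more patients per cohort. Changing the test in section 7.2 to Boschloo's would raise power to about 73% with the same patients, with a maximum size of 4.3%. That still falls short of 80%, and the power figure in the new sentence would have to change to match.

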## **2.3 Number of patients**

- 32 patients in each cohort with 3:1 allocation ratio (24 etoposide and 8 control per cohort)
- 64 patients total

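### Section 7.1 treats any observed improvement as initial evidence of efficacy, without a threshold or a link to the test in section 7.2; an inert drug would meet that wording about 47% of the time per cohort

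*Combined protocol and SAP*

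**What the plan says.** Section 7.1 states that "The effect of the intervention will be evaluated in each cohort separately", with 24 patients on etoposide and 8 on control in each cohort (section 2.3 gives the same numbers). The endpoint is a "2 point improvement in respiratory status on an 8 point scale at Day 14". The control rate is assumed to be 30%, the alternative is an "80% response rate in the Etoposide group", and the design is said to have a two-sided α "of 0.05 and 80% power".

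The closing sentence of 7.1 then says the study is not powered for statistical significance and adds that "it will provide initial evidence of efficacy if improvement in response is observed". Improvement is not defined: no minimum size, confidence level or p-value is given.

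Section 7.2 plans, for the same endpoint, a 95% confidence interval for the difference in rates and Fisher's exact test, with all analyses at α = 0.05. Neither section says whether the phrase in 7.1 depends on that result.

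**The concern.** The sentence sets significance aside and names what will stand in its place, namely an improvement that is observed. Taken as written, a lead of one responder in 24 would allow the report to speak of evidence of efficacy. With only 8 controls, the observed control rate varies so much by chance that a lead of some size is close to a coin flip when the drug does nothing.

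The exposure is greater because the trial is open-label without placebo (section 4.1) and the investigator assesses the primary endpoint (section 10.1). What is at stake is the wording of the trial's conclusion: whether a numerical lead may be reported as evidence when the planned test shows nothing.

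**Working it through.** **Inputs.** 24 etoposide and 8 control per cohort (sections 2.3 and 7.1); control response 30%, alternative 80%, two-sided α = 0.05, power 80% (7.1); Fisher's exact test and 95% CI (7.2).

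**The plan's own figure.** The unpooled normal approximation has SE = √(0.3×0.7/8 + 0.8×0.2/24) = 0.1814. Power = Φ(0.5/0.1814 − 1.96) = Φ(0.796) = 78.7%, close to the stated 80%. Exact power of the planned two-sided Fisher test is 67.9%. The point below does not depend on which is used; it concerns the sentence that follows the power statement.

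**Chance of a lead when the drug is inert.** Let X ~ Bin(24, p) be etoposide responders and Y ~ Bin(8, p) control responders. Etoposide leads when X/24 > Y/8, that is, X > 3Y. With p = 0.30:

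| Y | P(Y) | P(X > 3Y) | Product |
|---|---|---|---|
| 0 | 0.0576 | 0.9998 | 0.0576 |
| 1 | 0.1977 | 0.9576 | 0.1893 |
| 2 | 0.2965 | 0.6114 | 0.1813 |
| 3 | 0.2541 | 0.1528 | 0.0388 |
| 4 | 0.1361 | 0.0115 | 0.0016 |
| 5 to 8 | | | <0.0001 |

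The sum is 0.469; an exact tie has probability 0.087. Across an assumed common rate of 5% to 80%, the chance of a lead stays between 43% and 48%.

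**Two cohorts.** If both enrol fully and are independent, the chance of a lead in at least one is 1 − (1 − 0.4686)² = 71.8%.

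**Interim rule.** Section 9.5 continues accrual if at least one treated patient responds. Requiring this as well, with 7, 8 or 10 treated patients at the interim, gives 44.5%, 45.4% or 46.3% per cohort. It removes little.

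**Comparison of criteria.** The same enumeration with other true rates, also for a minimum observed difference of 25 points (X − 3Y ≥ 6) and for a two-sided Fisher p ≤ 0.05 favouring etoposide:

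| True rates, etoposide vs control | Any lead | At least 25 points | Fisher, favouring etoposide |
|---|---|---|---|
| 20% vs 30% | 26.2% | 2.7% | 0.07% |
| 30% vs 30% | 46.9% | 10.8% | 0.95% |
| 50% vs 30% | 82.4% | 45.3% | 11.2% |
| 60% vs 30% | 92.3% | 65.4% | 24.6% |
| 80% vs 30% | 99.4% | 92.5% | 67.9% |

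Under the 30% null, the wording in 7.1 and the test in 7.2 differ by a factor of about 49 (46.9/0.95).

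For the 25-point rule, the largest false-signal probability over all common rates is 13.3% per cohort, near a rate of 51%. For at least one of two cohorts it is 1 − (1 − 0.1084)² = 20.5% at 30%, and 1 − (1 − 0.1331)² = 24.8% at the maximum.

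**Example.** 7/24 versus 2/8 is a lead of 29.2 − 25.0 = 4.2 points. It meets the sentence in 7.1, yet Fisher's p is 1.0.

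**The case against.** The strongest reply is that the sentence is a caveat and not a decision rule. It closes a sample-size section, opens by conceding limited power, and is not referred to again. The analysis itself is in 7.2, which has a stricter standard for the same endpoint, and the planned interval would expose a trivial lead for what it is.

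Much of this stands, and it rules out several stronger readings that a reader might infer:

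- *That the trial has a 47% type I error, or that the plan contains no stricter criterion.* It does contain one: section 7.2 keeps Fisher's exact test at α = 0.05, which favours etoposide 0.95% of the time under the 30% null.
- *That a one-point difference would qualify.* Differences come in steps of 1/24, so the smallest positive one is 4.2 points.
- *That 72% applies in any event.* Cohort 2 opens only with the COVID Research Committee's permission (section 4.2). If only cohort 1 runs, 46.9% applies. Section 7.1 also makes no claim based on success in either cohort.
- *That a chance lead would trigger further treatment.* Nothing in the documents makes treatment, accrual or the opening of cohort 2 depend on this sentence. Sections 4.2, 9.5 and 10.2 govern accrual and cohort opening, and none states a between-arm efficacy criterion.

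What the reply does not remove is the missing link. The sentence offers observed improvement precisely because significance is not expected, so pointing to 7.2 does not show that the test governs the phrase. A report could follow both sections, find p = 1.0, and still claim initial evidence of efficacy.

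**Conclusion.** The concern holds as a defect in how the plan turns its result into a conclusion. Read as any etoposide rate above control, the wording in 7.1 is met by an inert drug 46.9% of the time per cohort at 30% response, and by a drug that lowers response from 30% to 20% in 26.2% of cohorts. The 71.8% figure for at least one cohort requires both to enrol fully and to be independent.

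Two assumptions carry this: the reading of improvement as any lead, which the text permits because it sets no threshold, and a common response rate of 30%, which matters little between 5% and 80%.

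The point deserves correction but is not among the most serious kind. The planned test, its α, the intention-to-treat population and the reported estimates are all unaffected.

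**What to change.** Replace the last sentence of 7.1 with wording such as:

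> *Within each cohort, any conclusion about efficacy will rest on the 95% confidence interval for the difference in Day 14 response rates and on Fisher's exact test, as set out in section 7.2. A higher observed rate with etoposide that falls short of this will be reported as inconclusive, with its confidence interval.*

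If the sponsor wants a looser screening signal for planning later work, it should pre-specify a minimum difference, label it non-confirmatory, state how it sits beside the test in 7.2, and give its operating characteristics per cohort and across both. A 25-point minimum is one possible choice, not one derived from the documents; its properties are in the table above. Results exactly at that cut-off have Fisher p-values from 0.056 to 0.41, so it cannot serve as a substitute for the test.

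The change is one sentence and needs no extra patients. The price is sensitivity to modest effects: at 50% versus 30%, the chance of calling a signal falls from 82.4% for any lead to 45.3% with the 25-point rule and 11.2% with Fisher's test.
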